12.4. Collection and Recording of Adverse Events

12.4.1. Collection Period

Adverse events will be collected from the time of consent until a participant completes study participation or until 30 days after he/she prematurely withdraws (without withdrawing consent) or is withdrawn from the study.

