3.1. Description of Study Design

Potential participants will be screened during an 8-week screening period. An esophagogastroduodenoscopy (EGD) with biopsies will be performed to determine study eligibility, and participants will be enrolled based on the presence of active disease and their ability to meet the study inclusion and exclusion criteria. Qualifying participants will be blindly randomized 1:1 to either study drug

(dupilumab) or placebo and will receive 600 mg once followed by 300 mg doses every two weeks of study treatment (for a total of 6 injections). During the treatment period, participants will be monitored for adverse events/reactions and will complete patient reported outcome metrics to track their symptoms and general wellbeing. At the end of the 12-week randomized treatment period (EOT), a repeat endoscopy with biopsies will be performed to assess the change in gastric eosinophil count from pre-to-post treatment. Participants and site study staff will remain blinded to the endoscopy biopsy results until all participants have completed the DBP EOT visit. Study participants who complete the 12-week treatment phase (whether on drug or placebo) will have the option to continue into an open-label extension (OLE) and laboratory studies and patient reported outcomes will be completed as indicated in the schedule of activities (SOA). The OLE ensures that every participant gets access to the drug and will provide data on the effect of a longer treatment period in comparison to the initial 12 weeks in the double-blind phase. A final study EGD will be performed two weeks after the last dose of the study drug. All participants will be followed for an additional 12 weeks after the last dose of study drug regardless of whether they participate in the OLE. A summary of the protocol is depicted in Figure 1.

[figure not shown]

Figure 1. Schematic summary of clinical trial.

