Week (W)	W-8 to 0	0	2	4	6	8	10	12/0	2	4	6	8	10	12	14	16	18	20	22	24	36
Window (days [d])	---	---	±3d	±3d	±2d	±3d	±2d	±3d	±3d	±2d	±3d	±2d	±2d	±3d	±2d	±2d	±3d	±2d	±3d	±2d	±3d
Patient global impression of change (PGI-C)					x		x	x		x		x		x		x		x		x	
Clinician global impression of severity (CGI-S)		x			x		x												x		
Clinician global impression of change (CGI-C)					x		x												x		
Safety																					
Vital Signs, Weight	x	x	x	x	x			x	x				x						x		
Height	x								x										x		
Physical Exam £	x	x	x					x											x		
Adverse Events	x	x	x	x	x			x	x	x	x		x		x		x		x	x	
Laboratory Testing																					
Serum chemistry	x	x						x					x						x		
CBC with differential ²	x	x	x	x	x			x	x	x ²			x		x ²				x		
Iron Panel	X							x											x		
Urinalysis	x	x						x					x						x		
Pregnancy test (or serum FSH)	Serum	Urine	Urine	Urine	Urine			Urine	Urine				Urine						Urine		
Biomarkers and Genomics																					
Biomarker blood and total IgE	x	x						x					x						x		
Blood DNA		x																			

¹Only participants who elect to continue into OLE will have eligibility re-checked by investigator, and administration of study drug. ²Will occur in local laboratory when not associated with visit. ³Home administration ⁴After confirming participant still meets inclusion/exclusion criteria, immediately contact the pharmacist to randomize the participant.

*End of treatment/early withdrawal visit (participants who withdraw will be asked to undergo end of treatment assessments).

**Follow-up should occur 12 weeks after the last injection (includes participants that withdraw prior to end of treatment).

‡Distribute to participants ≥18

†Distribute to participants ages 8-17.

§ Although technically validated for ≥18, distribute to participants of all ages.

£ A full physical exam will be conducted at screening and early withdrawal. Brief targeted physical exams will be performed at subsequent visits and when an AE is reported at any visit.

V, visit encounter. T, telephone encounter.

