8.4.3. Study Visit During Follow-up Period (12 weeks)

All participants will be followed for 12 weeks after the last dose of the study drug or placebo.

Telephone Visit 3 (Week 36 ± 3 days)

- AEs
- Pregnancy assessment
- End of study

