11.1. Participant Completion

The primary outcome is reached when a participant completes the visit 5 EGD at the end of the double-blind phase. Participants complete study participation when they have completed the end of study (EOS) telephone check-in.

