12.4.3. Recording Adverse Events

Throughout the study, the investigator will record adverse events and serious adverse events as described previously (Section 12.2, *Definitions*) on the appropriate paper AE/SAE CRF regardless of the relationship to study therapy regimen or study procedure.

Once recorded, an AE/SAE will be followed until it resolves with or without sequelae, or until the end of study participation, or until 30 days after the participant prematurely withdraws (without withdrawing consent)/or is withdrawn from the study, whichever occurs first.

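### Adverse event collection closes 30 days after study withdrawal, usually before the 12-week adverse event contact scheduled for the same participants

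*Protocol*

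**What the plan says.** Two parts of the protocol set the end of AE observation for participants who leave early.

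**The 30-day rule**
- Section 12.4.1 starts collection at consent and ends it at completion of participation or, for early leavers, "until 30 days after he/she prematurely withdraws (without withdrawing consent) or is withdrawn from the study".
- Section 12.4.3 follows a recorded event to resolution, to the end of participation, "or until 30 days after the participant prematurely withdraws (without withdrawing consent)/or is withdrawn from the study, whichever occurs first".

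**The 12-week rule**
- The footnote to Table A in section 8.1.6 reads: "Follow-up should occur 12 weeks after the last injection (includes participants that withdraw prior to end of treatment".
- Section 8.4.3 says: "All participants will be followed for 12 weeks after the last dose of the study drug or placebo". It lists AEs among the items of Telephone Visit 3.
- Section 3.1 says: "All participants will be followed for an additional 12 weeks after the last dose of study drug regardless of whether they participate in the OLE". The SAP's overview of the study design repeats this.
- Section 11.1 defines completion: "Participants complete study participation when they have completed the end of study (EOS) telephone check-in". The protocol glossary places that call 12 weeks after the last dose.

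The SAP does not settle the matter. Its safety endpoints cover all AEs. Its safety outcomes section tabulates them by treatment group as numbers and percentages with exact intervals, and gives no cut-off date.

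**The concern.** A site that telephones a withdrawn participant at 12 weeks is told by section 8.4.3 to ask about AEs. Section 12.4.1 tells the same site that the collection period for that participant has normally closed. One site may record what it hears and another may not, and both could say that they followed the protocol.

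Two things are at stake. The first is whether late events in withdrawn participants reach the database at all. The second is comparability: AE percentages by arm take no account of observation time, so a shorter window for withdrawals than for completers would pass into the tables without being visible there.

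**Working it through.** The plan gives no figure of its own to reproduce here. The check is calendar arithmetic, followed by a reading of who falls under each rule.

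**Inputs**
- Scheduled AE contact: 12 weeks after the last injection (Table A footnote, section 8.4.3), so 12 × 7 = 84 days.
- Visit window: ±3 days (Table A, section 8.4.3), so day 81 to day 87.
- End of collection: 30 days after withdrawal (section 12.4.1).
- k: days from last injection to withdrawal. The documents do not give it. I use 0, 14 and 28 days, that is none, one and two of the two-week dosing intervals in section 3.1.

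**Formula**

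The two clocks start at different points: one at withdrawal, the other at the last injection. Put on one scale, collection closes on day k + 30 after the last injection. The uncovered time before the contact is 84 − (k + 30) = 54 − k days.

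| k (assumed) | Collection closes | Gap to day 84 | Gap to day 81–87 | Gap as share of 84 days |
|---|---|---|---|---|
| 0 | day 30 | 54 days | 51–57 | 54/84 = 64% |
| 14 | day 44 | 40 days | 37–43 | 40/84 = 48% |
| 28 | day 58 | 26 days | 23–29 | 26/84 = 31% |

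The gap reaches zero only at k = 54 or more.

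**Who falls under both rules**
- *Left or was removed from the study, consent not withdrawn:* both rules apply and they conflict.
- *Stopped injections but stayed for assessments (sections 11.1.2 and 11.2):* not withdrawn, so collection runs to the end-of-study call. No conflict.
- *Withdrew consent:* the voluntary-withdrawal part of section 12.4.1 excludes them. Section 11.1.2 then allows only information on AEs related or potentially related to the study. No conflict.
- *Missed more than one dose:* section 11.1.1 (item 15) lists this as a possible ground for ending study participation, while section 11.2 keeps these participants in the study. Their AE window depends on which section a site follows, so these sections also need reconciling.

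**Is there a reading without conflict?**

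The rules cannot be assigned to different groups, because the Table A footnote names early withdrawals. Section 12.4.1 joins its two end-points with a plain alternative and does not say that the earlier one prevails; section 12.4.3 does say so. One could therefore argue that collection in a withdrawn participant runs on to the call. But then the 30-day limit would usually have no function. The natural reading is that collection closes at 30 days. The accurate conclusion is that the handling of later events is unclear, not that they are certainly discarded.

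**The case against.** The strongest case on the other side is that this is a wording mismatch with little consequence. It has five parts.

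1. *Size.* A reader might infer a fixed loss of 54 of 84 days. That holds only if withdrawal falls on the day of the last injection. The gap shrinks day for day with k, and k is unknown.
2. *Reach.* A reader might infer that anyone who stops drug because of a problem gets the shorter window. The 30-day limit attaches to leaving the study, not to stopping injections, and sections 11.1.2 and 11.2 provide for staying in. Still, section 11.1.1 lists several safety grounds for ending study participation, among them related higher-grade AEs, anaphylaxis, suspected serum sickness and vasculitis. Some participants who leave for safety reasons would therefore fall under the limit, and section 12.4.3 could end follow-up of an unresolved event before the 12-week call.
3. *Direction.* A reader might infer that events are undercounted where they are most likely. The documents do not support this. The event that leads to withdrawal happens before it and is collected, as is anything in the next 30 days. Nothing in the documents says that later events are more frequent in withdrawn participants.
4. *SAP.* The SAP reports all AEs and excludes nothing at 30 days. That is correct, but it can only tabulate what was recorded, and recording is governed by section 12.4.
5. *Numbers.* The SAP section on changes from the protocol reports one dropout before the end of the double-blind phase, in the placebo arm. Everyone in the extension receives dupilumab, so no concurrent placebo comparison is at risk there.

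These points limit the size and reach of the problem. They do not remove the conflict between the sections.

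**Conclusion.** The concern holds as an internal inconsistency in the safety data rules. For participants who leave the study without withdrawing consent, sections 12.4.1 and 12.4.3 end AE collection and follow-up 54 − k days before a contact that the protocol requires and at which AEs are to be recorded. The result rests on the natural reading of section 12.4.1 and on assumed values of k.

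A reader might go further and infer that the double-blind AE comparison is biased. The documents do not support that: with a single placebo dropout reported, the effect there is likely small. The number of withdrawals in the extension is not reported, so the effect on its AE summaries cannot be sized. The point is still worth correcting, because it decides which safety data are recorded and counted.

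**What to change.** - **Protocol.** Reconcile sections 12.4.1 and 12.4.3 with sections 3.1 and 8.4.3 and the Table A footnote, so that AEs reported at the follow-up contact already scheduled are recorded for every participant who has not withdrawn consent.
- **SAP, safety outcomes.** State the AE cut-off used, and say that events reported at that contact by withdrawn participants are counted.
- **Timing.** The latest SAP revision was made after imputed and complete-case results had been compared, so a protocol edit may now change little of what is collected in the double-blind phase. In that case the SAP or the study report should state which cut-off was applied in practice and whether such events were included.

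The cost is wording only. The call is already in the schedule, and no visit or procedure is added.

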12.4.2. Collecting Adverse Events

Adverse events (including SAEs) may be discovered through any of these methods:

- Observing the participant.
- Interviewing the participant [e.g., using a checklist, structured questioning, diary, etc.] .
- Receiving an unsolicited complaint from the participant.
- Reviewing the participant's electronic medical record during study participation.
- In addition, an abnormal value or result from a clinical or laboratory evaluation can also indicate an adverse event, as defined in Section 12.3, *Grading and Attribution of Adverse Events*.

12.4.3. Recording Adverse Events

Throughout the study, the investigator will record adverse events and serious adverse events as described previously (Section 12.2, *Definitions*) on the appropriate paper AE/SAE CRF regardless of the relationship to study therapy regimen or study procedure.

Once recorded, an AE/SAE will be followed until it resolves with or without sequelae, or until the end of study participation, or until 30 days after the participant prematurely withdraws (without withdrawing consent)/or is withdrawn from the study, whichever occurs first.

12.5. Reporting of Serious Adverse Events and Adverse Events

12.5.1. Reporting of Serious Adverse Events to Sponsor ([name])

This section describes the responsibilities of the site investigator to report serious adverse events to the sponsor ([name], PhD) via paper CRFs, facsimile, electronically, or by phone. Timely reporting of adverse events is required by 21 CFR and ICH E6 guidelines.

Site investigators will report to the sponsor ([name], PhD) and the IPM all serious adverse events (see Section 12.2.4, *Serious Adverse Event*), regardless of relationship or expectedness within 24 hours of discovering the event.

For serious adverse events, all requested information on the AE/SAE paper CRF will be provided. However, unavailable details of the event will not delay submission of the known information. As additional details become available, the paper AE/SAE CRF will be updated and submitted.

Additionally, All SAEs, regardless of assessment of causal relationship to study drug, must be reported to Regeneron within 24 hours.

Fax SAE/CIOMS or MedWatch Reports to [contact]

Email Form: [contact]

Information not available at the time of the initial report must be documented in a follow-up report. Substantiating data such as relevant hospital or medical records and diagnostic test reports may also be requested.

12.5.2. Reporting of Unexpected and Study-Related Non-Serious Adverse Events

An unexpected, non-serious adverse event that is of Grade 2 severity or higher and study related will be recorded and reported to the sponsor and IPM under the serious adverse event reporting procedure above (i.e., within 24 hours).

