5.1. Risks of Investigational Product as cited in Investigator Brochure or Package Insert

There are no known serious side effects including infection risks in patients taking dupilumab based on existing data (see package insert ¹⁶ and investigator brochure). Based on trials to date, common adverse events (occurring in 10% or less of participants) include eye issues (e.g., conjunctivitis, blepharitis, keratitis, dry eyes), oral and other herpes simplex infections and injection site reactions. These were consistently mild-moderate and occurred with similar frequency between the treatment and placebo groups ¹⁶.

Conjunctivitis and keratitis occurred more frequently in atopic dermatitis participants who received dupilumab. Conjunctivitis was the most frequently reported eye disorder. Most participants with conjunctivitis recovered or were recovering during the treatment period. Keratitis was reported in <1% of the dupilumab group (1 per 100 subject-years) and in 0% of the placebo group (0 per 100 subject-years) in the 16-week monotherapy trials. In the 52-week dupilumab plus topical corticosteroids (TCS) trial, keratitis was reported in 4% of the dupilumab plus TCS group (12 per 100 subject-years) and in 0% of the placebo plus TCS group (0 per 100 subject-years). In the recent phase II EoE dupilumab study, conjunctivitis and keratitis were not seen. Study PIs should refer participants to an ophthalmologist for any clinically significant ocular condition that develops during study participation. Based on post- marketing safety data, events of angioedema, arthralgia, keratitis and ulcerative keratitis are now considered adverse drug reactions (ADRs).

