11.4. Study Stopping Rules

Study enrollment will be suspended pending Study Sponsor, DAIT NIAID, the central IRB and NIAID Allergy and Asthma DSMB expedited review of all pertinent data if any of the following occur:

- 1 death that is possible related/related to dupilumab
- One Grade 4 adverse event based on CTCAE 5.0 grading that is possibly related/related to dupilumab
- Two or more participants have a Grade 3 adverse event based on CTCAE 5.0 grading that is possibly related/related to dupilumab
- Two or more participants have a Grade 4 adverse events based on AEC grading (Section 12.3.1, Table B) that are possibly related/related to dupilumab.

The study may not be resumed until all pertinent information is discussed with the Study Sponsor, IPM, DAIT NIAID, NIAID Allergy and Asthma DSMB, and the central IRB, and all parties concur with the resumption of the study. Local IRBs will be informed of the study stoppage and the DSMB/Central IRB's decision on resumption of the study. The study may be terminated by DAIT/NIAID or the NIAID Allergy and Asthma DSMB upon review of any observations, events, or new information that merits such action. If the study is suspended or terminated, the Sponsor/principal investigator will notify the drug manufacturer, and regulatory agencies and the IRB will be notified as appropriate. Additionally, the study entry on clinicaltrials.gov will be updated to reflect that the study has been discontinued.

12. Safety Monitoring and Reporting

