12.3. Grading and Attribution of Adverse Events

12.3.1. Grading Criteria

The study site will grade the severity of adverse events experienced by the study participants, with the exception of peripheral eosinophilia, according to the criteria set forth in the National Cancer Institute’s Common Terminology Criteria for Adverse Events (CTCAE; version 5.0; November 27, 2017). This document (referred to herein as the NCI-CTCAE manual) provides a common language to describe levels of severity, to analyze and interpret data, and to articulate the clinical significance of all adverse events. The NCI-CTCAE has been reviewed by the study sponsor study sponsor ([name], PhD) and has been deemed appropriate for the participant population to be studied in this protocol.

Adverse events will be graded on a scale from 1 to 5 according to the following standards in the NCI-CTCAE manual. A semicolon indicates ‘or’ within the description of the grade.

Grade 1 = mild; asymptomatic or mild symptoms; clinical or diagnostic observations only; intervention not indicated

Grade 2 = moderate; minimal, local or noninvasive intervention indicated; limiting age-appropriate instrumental activities of daily living (ADL) (e.g., shopping, preparing meals, using the phone, etc.)

Grade 3 = severe or medically significant but not immediately life-threatening; hospitalization or prolongation of hospitalization indicated; disabling; limiting self-care ADL (e.g., bathing, dressing, feeding self, etc.)

Grade 4 = life-threatening consequences; urgent intervention indicated

Grade 5 = death related to AE.

AE’s will be recorded on the appropriate AE paper case report for this study.

For grading an abnormal value or result of a clinical or laboratory evaluation (including, but not limited to, a radiograph, an ultrasound, an electrocardiogram etc.), a treatment-emergent adverse event is defined

as an increase in grade from baseline. Changes in grade from screening to baseline will also be recorded as adverse events but are not treatment-emergent. If a specific event or result from a given clinical or laboratory evaluation is not included in the NCI-CTCAE manual, then an abnormal result would be considered an adverse event if changes in therapy or monitoring are implemented as a result of the event/result.

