12.8. Review of Safety Information

12.8.1. Independent Protocol Monitor (IPM) Review

The IPM will receive notification of all SAEs within 24 hours of notification by the Investigator and will make decisions on expedited safety reporting. The DAIT/NIAID medical officer will be notified about the event and the decision on expedited safety reporting within 24 hours of the IPM decision.

The IPM will receive monthly reports from the Data Center compiling new and accumulating information on AEs. The Sponsor, Medical Vigilance Solutions and DAIT/NIAID medical officer will also receive these monthly reports.

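### The Section 11.4 stopping rules count related events whatever their seriousness or expectedness, but the 24-hour reporting rules leave out one narrow class of them, which can delay an enrolment halt by up to about one monthly cycle

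*Protocol*

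**What the plan says.** **Triggers.** Protocol Section 11.4, repeated in the synopsis, suspends enrolment pending expedited review when any of four conditions is met. The one for Grade 3 reads: "Two or more participants have a Grade 3 adverse event based on CTCAE 5.0 grading that is possibly related/related to dupilumab". The other three carry the same relatedness condition: a single death, a single event at CTCAE Grade 4, and Grade 4 on the eosinophil scale of Table B in at least two participants. No trigger mentions seriousness or expectedness.

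**Fast reporting.** Section 12.5.1 requires sites to report every serious adverse event to the sponsor and the IPM "regardless of relationship or expectedness within 24 hours of discovering the event". Section 12.5.2 applies the same procedure to one further group: "An unexpected, non-serious adverse event that is of Grade 2 severity or higher and study related". All three conditions must hold.

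**Routine reporting.** Section 12.4.3 has all other adverse events recorded on a paper form and gives no deadline for sending it. Section 12.8.1 then says: "The IPM will receive monthly reports from the Data Center compiling new and accumulating information on AEs". The sponsor and the DAIT/NIAID medical officer receive the same reports. Section 6.4 has listings reviewed monthly or more often. Planned DSMB reviews are annual (Section 12.8.2.1).

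**Effect of a trigger.** Sections 12.8.2.2 and 12.8.2.2.1 provide for an ad hoc DSMB review and a halt to new consents and to treatment initiation in screened participants. Participants already on therapy continue treatment.

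**The concern.** A stopping rule can act only once someone with authority to apply it knows that its condition has been met. Here the rule and the reporting that feeds it use different criteria: Section 11.4 sorts events by grade and relatedness, while Sections 12.5.1 and 12.5.2 sort them by seriousness and expectedness. An event can satisfy the first pair and fail the second.

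The two-participant rules add a further difficulty. The trial is multi-center. Each site sees its own participants, and no section assigns anyone a running count against Section 11.4. Final attribution rests with the sponsor after consulting the IPM and DAIT/NIAID (Section 12.3.2), so the sponsor has to learn of the event before the rule can be applied.

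What is at stake is that new participants could be consented and started on treatment, and DSMB review postponed, after the protocol's own halt condition has been met and with every site following the plan as written.

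**Working it through.** No sample size, power or error rate is involved. The check crosses the triggers with the reporting routes.

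**Step 1. Which events count.** Under Section 11.4: CTCAE Grade 4 (one event), CTCAE Grade 3 (two or more participants) and Table B Grade 4 (two or more participants), each possibly related or related. Section 12.3.1 applies CTCAE grading "with the exception of peripheral eosinophilia", so Grade 3 eosinophilia on Table B falls under no trigger. A related death is always a serious adverse event and is therefore always reported within 24 hours.

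**Step 2. Route for each kind of counting event.**

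| Event counting toward 11.4 | Unexpected | Expected at that severity |
|---|---|---|
| Serious | 24 hours (12.5.1) | 24 hours (12.5.1) |
| Non-serious | 24 hours (12.5.2) | Monthly report or listing (12.8.1, 6.4) |

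All four cells count toward the rules. One of the four has no 24-hour route.

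**Step 3. Whether that cell can be occupied.** Section 12.3.1 defines Grade 3 by alternatives, one of which is limitation of self-care, so Grade 3 does not require hospitalisation and need not be serious. Section 5.1.1 describes hypersensitivity reactions to the drug as possibly severe, so a Grade 3 reaction of that kind, managed without admission, could be judged both expected and non-serious. The documents allow this but do not establish it. Listed severities are in the Investigator Brochure and package insert, which are not available here.

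**Step 4. Length of the delay.**

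- 24-hour routes: 1 day from discovery.
- Routine route: up to one monthly cycle, at most 31 days, plus the time to submit and enter the paper form, which the protocol does not bound.
- If such events fell evenly over a 31-day cycle (an assumption), the mean wait would be 31 / 2 = 15.5 days before form-handling time.

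A two-participant rule is delayed if the event completing the count is in the uncovered cell. It is also delayed if an earlier counting event is in that cell and has not yet appeared in a report when the completing event occurs.

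**Step 5. Whether another section closes the gap.** Section 6.5 stops treatment and Section 11.1.1 allows withdrawal for the affected participant, but neither sets a notification time. Section 12.8.2.2 lets the sponsor, IPM or medical officer request an ad hoc review, but they must first know of the event. No other section supplies a faster route.

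**The case against.** The strongest reply is that the uncovered class is small. Section 12.2.3 treats an event as unexpected when it is listed at a different specificity, severity or rate. Section 5.1 calls the common listed events, including eye disorders and injection site reactions, consistently mild to moderate. On that text, a Grade 3 event of those kinds exceeds its listed severity and is reportable within 24 hours, so neither is a sound example of the gap. Section 5.1 also names ulcerative keratitis and angioedema as recognised reactions, but gives no severity and so does not show that a Grade 3 case is expected. Grade 4 is defined by life-threatening consequences, close to a criterion for a serious event in Section 12.2.4, so most Grade 4 events would go by the serious route. Table B Grade 4 eosinophilic disease could qualify as an important medical event under the same section without admission. All of this stands and limits how often the gap would matter.

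It is also fair that the Data Center does compile events across sites, that monthly is the minimum review frequency, and that the Manual of Procedures, which is not available here, may say more. Compilation at monthly intervals still leaves the delay in place, and the protocol itself gives no faster route.

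A reader might infer three stronger points that the documents do not support:

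- **Extra doses.** With dosing every two weeks, a month's delay looks like about two avoidable doses per treated participant. Section 12.8.2.2.1 continues treatment during a halt, so prompt detection would not by itself prevent those doses.
- **All severe related events are affected.** Table B Grade 3 is not a trigger, CTCAE Grade 3 needs two participants, and three of the four cells are covered.
- **Nobody sees the event.** The site knows of it and must act on that participant under Section 6.5. It is the sponsor, IPM and DSMB who may not know.

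**Conclusion.** The mismatch is real and narrow. Related, non-serious events that are expected at the observed severity count toward Section 11.4 but have no 24-hour route. For that class, the halt on new consents and treatment initiations, and the ad hoc DSMB review, can be delayed by up to about one monthly cycle, or longer if the paper form is slow, against one day elsewhere. The two-participant rules are the most exposed.

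The delay figure assumes that reports are issued monthly and no sooner. The number of participants who might be consented or randomised in that time cannot be given, because the documents state no accrual rate. Nor can the frequency of such events, which depends on reference safety information outside the documents. The case for acting rests on the low cost of closing the gap, not on a claim that it will often be used.

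**What to change.** Add one sentence to Section 12.5.2: any adverse event that counts toward a rule in Section 11.4 (possibly related or related, and CTCAE Grade 3 or higher or Table B Grade 4 or higher) is reported to the sponsor and IPM within 24 hours of discovery, whether or not it is serious or expected. The site investigator's initial attribution should be enough to start the report.

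Name the IPM, or the Data Center, as keeper of the running count across sites against Section 11.4. The count needs no treatment codes, so blinding under Sections 3.6 and 13.4 is undisturbed.

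The stopping thresholds and the participant-level rules in Sections 6.5 and 11.1.1 stay as they are. The cost is a one-sentence amendment, a line in the Manual of Procedures, and a few extra expedited reports across about 40 participants.
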